9.5 Data and Safety Monitoring

Study Investigators will conduct continuous review of data and patient safety. The Investigator will submit quarterly progress reports of these data to the Clinical Trials Monitoring Committee for review. The review will include for each treatment arm/dose level: the number of patients enrolled, withdrawals, significant toxicities as described in the protocol, serious adverse events both expected and unexpected, dose adjustments, and responses observed. The PI

ULEU-13049 32 Version date: 09Aug2017

maintains a database of all adverse events with toxicity grade and information regarding treatment required complications, or sequelae. The Investigator will submit a copy of the AE spreadsheet along with the Progress Report to the Clinical Trials Monitoring Committee for review.

- Any serious adverse event that is serious, related AND unexpected must be reported within 10 calendar days to both the DSMC and the RSRB (see RSRB guidelines).
- Serious adverse events that are related AND expected or unrelated AND unexpected will be reported to the Committee for review at the quarterly meeting. SAE reports are expected to include sufficient detail so that the DSMC can determine the severity, toxicity grade, expectedness, treatment required, and a follow up report documenting resolution or if there are sequelae. Unless otherwise specified in the protocol, serious adverse events that require detailed reports (but not necessarily expedited) are expected, related, non-hematologic toxicities of grades 3, 4 or 5.

The Data Safety Monitoring Committee provides oversight of study progress and safety by review of accrual and events at regularly scheduled meetings. The frequency of review is determined by the size, risk and complexity of the trial, and is assigned by the Protocol Review Committee at the time of their initial review and approval. The Data and Safety Monitoring Committee will monitor all adverse event rates utilizing a cumulative spreadsheet listing of all events submitted along with progress reports by the PI. All serious adverse events that have occurred in the prior 3 months will be reviewed at the regular quarterly meeting of the DSMC in order to confirm toxicity grade, expectedness, relatedness, sequelae, follow up required, and risk to current or future subjects.

Events that are serious, unexpected and related will require expedited review within 10 calendar days to the Safety Coordinator. The DSMC Chair will determine whether further action is required, and when patient safety is of concern, an interim meeting may be called.

ULEU-13049 33 Version date: 09Aug2017

11.0 STATISTICAL CONSIDERATIONS

Based on the data of Cashen¹⁵, where response rate to single agent decitabine was about 25 %, our null hypothesis would be that the true response rate r to the combination therapy is less than 25% (i.e. $H_0:r \le 0.25$). We will use Simon's two-stage design to test this null hypothesis against its one-sided alternative ($H_1:r > 0.25$). Assume that the true response rate in fact exceeds 50%. A maximum of 24 evaluable patients would give 80% power to reject the null hypothesis at a significance level of .05. In the first stage of the phase II study, 9 patients will be initially enrolled to assess the response rate to the combination therapy. If there are 2 or fewer of the 9 patients have responded, the phase II study is stopped for accrual and the combination therapy is determined not active. The probability of this early termination is 60%. If at least 3 out of the first 9 evaluable patients respond in the first stage, 15 additional evaluable patients will be accrued for a total of 24 evaluable patients. The null hypothesis is rejected if 10 or more responses are observed in 24 patients.

The ribavirin dose escalation arm of this study will be a phase I dose escalation plan, so only tabular descriptions of toxicity and outcomes will be generated. The design of the phase I portion of the study is a standard 3+3 up and down design (See Section 7 for details). A minimum of 3 and a maximum of 6 patients will be entered at each dose level. The starting dose level as well as each subsequent dose increment (decrement) will be pre-specified. The first 3 patients will be treated at the starting dose level. If none of the 3 patients experiences dose-limiting toxicity, the dose will be escalated to the next higher level, and another 3 patients will be treated at the escalated level. However, if 1 of the first 3 patients experiences a dose-limiting toxicity, three more patients will be treated at the same dose level. The dose escalation continues until at least two patients among 3 or 6 patients experience toxicities, or until the highest prespecified dose level is reached. The MTD is defined as the highest dose level for which at least 5 of 6 subjects did not experience a DLT. Once the MTD has been established, the study will subsequently expand to a phase II study at the MTD level to obtain further safety and efficacy data. The Data Safety and Monitoring Board of the JP Wilmot Cancer Center will be utilized to review the data between cohorts and prior to escalating from phase I to a phase II portion of the study.

As noted in section 8, the correlative studies will be primarily exploratory. We will utilize a Chi square method to determine a correlation between clinical response and mTOR mediator inhibition as assessed by p70S6 kinase expression or 4EBP1 expression. Both response (yes/no) or decreased expression (yes/no) will be treated as binary variables, and decreased expression will be defined as at least a 25% decrease by densitometry or flow cytometric measurement. We will also determine the mean decrease in expression in the responding and non-responding groups for further descriptive correlations. In the treatment arm with ribavirin, similar analysis will be performed for eIF4E expression.

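### Section 11.0 names only a chi-square for the response-by-marker tables, although the planned tables are too sparse for it; an exact test should be named instead.

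*Combined protocol and SAP*

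**What the plan says.** Section 11.0 sets up a two-by-two table for the correlative work, with response and marker decrease each reduced to yes or no. The marker cut-off is explicit: "decreased expression will be defined as at least a 25% decrease by densitometry or flow cytometric measurement". The test is stated as: "We will utilize a Chi square method to determine a correlation between clinical response and mTOR mediator inhibition". For Arm B, "In the treatment arm with ribavirin, similar analysis will be performed for eIF4E expression".

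The section does not say whether a continuity correction applies. It gives no exact alternative and no significance level for these analyses. It does state that "the correlative studies will be primarily exploratory", and it adds a summary without a test: "We will also determine the mean decrease in expression in the responding and non-responding groups for further descriptive correlations".

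The table sizes follow from the same section. In Arm A, "If there are 2 or fewer of the 9 patients have responded, the phase II study is stopped for accrual"; otherwise 15 more evaluable patients bring the total to 24. In Arm B phase I, "A minimum of 3 and a maximum of 6 patients will be entered at each dose level".

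**The concern.** The chi-square p-value relies on a large-sample approximation that is poor when expected cell counts are small. The plan's own stopping rule produces such tables: a stopped Arm A has 9 patients and at most 2 responders. Section 8.0 also warns that cells for the later assays may run short, so usable tables may be smaller still.

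At stake is whether an exploratory association is reported as strong evidence when it rests on one patient. With no stated level or power for these analyses, a very small p-value has nothing beside it to temper it.

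**Working it through.** **Inputs from Section 11.0.** Stage 1 n = 9; stop at 2 or fewer responders; total N = 24; reject at 10 or more; response rates 0.25 (null) and 0.50 (alternative); stated early-stopping probability 60%.

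**Assumptions, not in the documents.** Uncorrected (Pearson) statistic; two-sided 5% level; true share q of patients with decreased expression, varied because no value is given; marker independent of response under the null.

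**1. The plan's own figure.** P(0, 1 or 2 responders of 9 at 0.25) = 0.0751 + 0.2253 + 0.3003 = 0.6007, matching the stated 60%. The full rule has type I error 0.0485 and power 0.8055, in line with the stated .05 and 80%. The response design is sound.

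**2. Sparseness.** Expected count = row total × column total / n.
- n = 9: the smallest expected count is at most 4 × 4 / 9 = 1.78, so all 64 possible pairs of margins have one below 5. With 2 responders, no responder cell can expect more than 2 × 8 / 9 = 1.78.
- n = 24 with 3 to 21 responders: 424 of 437 pairs of margins have an expected count below 5.

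**3. Single tables.** X² = n(ad − bc)² / (product of the four margins). Each table is given as decreases among responders v decreases among non-responders.

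| Table | X² | Chi-square p | Fisher p |
|---|---|---|---|
| 1/1 v 0/8 | 9 × 8² / (1 × 8 × 1 × 8) = 9.00 | 0.0027 | 1/9 = 0.111 |
| 1/2 v 0/7 | 9 × 7² / (2 × 7 × 1 × 8) = 3.94 | 0.047 | 2/9 = 0.222 |
| 4/8 v 2/16 | 24 × 48² / (8 × 16 × 6 × 18) = 4.00 | 0.0455 | 0.129 |

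With the margins fixed as in the second row, the chi-square rejects whenever the one decrease falls in a responder, so its true size is 2/9 = 22.2%. With the margins of the third row it is 12.9%.

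**4. Average size in stopped tables.** Sum over the number of decreases M ~ Binomial(9, q) and over the hypergeometric cell counts, counting X² > 3.841. Weight 1 and 2 responders by 0.2253/0.5256 = 0.429 and 0.3003/0.5256 = 0.571.

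Hand check with 1 responder at q = 0.20: rejection needs the responder to be among 1 or 2 decreases (the mirror cases add less than 0.0001). That gives 0.3020 × 1/9 + 0.3020 × 2/9 = 0.1007. With 2 responders the size is 0.0904. The average is 0.429 × 0.1007 + 0.571 × 0.0904 = 0.0948.

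| q (or 1 − q) | 0.05 | 0.10 | 0.15 | 0.20 | 0.25 | 0.30 | 0.40 | 0.50 |
|---|---|---|---|---|---|---|---|---|
| Size | 0.060 | 0.089 | 0.098 | 0.095 | 0.084 | 0.071 | 0.047 | 0.037 |

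Counting a stop with no responders as no rejection lowers these to 0.078, 0.083, 0.062, 0.041 and 0.033 at q = 0.1, 0.2, 0.3, 0.4 and 0.5.

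**5. Continued tables and the whole design (q from 0.1 to 0.5).** Given stage 2 (n = 24), size is 0.025 to 0.060. Over stop and continue together it is 0.042 to 0.067 at a 25% response rate and 0.031 to 0.058 at 50%.

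**6. Alternatives in stopped tables.** Fisher's test has size 0 with 1 responder and 0.002 to 0.008 with 2. With 1 responder its p-value cannot fall below 1/9. With 2 it reaches 0.05 only at perfect separation, p = 1/36 = 0.028. Mid-P at q of 0.1 to 0.5 averages 0.005 to 0.018. A Yates-corrected chi-square behaves like Fisher here, at most about 0.008.

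**The case against.** The strongest reply is that these analyses are labelled exploratory, carry no significance level and drive no decision. Mean decreases by response group will be reported alongside. Averaged over the design, even the uncorrected chi-square stays near 5%. All of this stands, and it limits the point to a wording change.

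Four stronger readings are tempting, and the documents do not support them.
- **That the plan specifies an uncorrected Pearson test.** It does not state the variant. A continuity-corrected test would be conservative in these tables. The gap is that the same sentence permits either.
- **That the error rate doubles whenever Arm A stops.** This needs roughly 10% to 25%, or 75% to 90%, of patients to show a decrease. At 40% to 60% the size is 3.7% to 4.7%, below nominal.
- **That p-values are generally wrong by a factor of 40.** That ratio (0.111/0.0027 = 41) belongs to the 1/1 v 0/8 pattern, measured against Fisher. Against Barnard's test (0.043) it is 16. The pattern has a probability of about 1% at q = 0.10 and a 25% response rate.
- **That objective 1.4 rests on this table.** In Section 1.0 that objective concerns baseline expression, and the synopsis adds in vitro effects. The chi-square concerns a decrease on treatment. Section 8.0 speaks of the feasibility of measuring inhibition and does not argue that inhibition explains response.

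For Arm B, nothing says that the eIF4E analysis would be done by dose level, so its table size is not known.

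**Conclusion.** The point holds in limited form. The only named test is unsuited to the tables that the plan will produce, and no fallback is given. If the uncorrected version is used at 5%, its size is about 4% to 10% in stopped Arm A tables with 1 or 2 responders at a 25% response rate, and about 3% to 7% over the whole design. The position within those ranges depends on the unknown marker-decrease rate. The case for change rests less on these averages than on individual sparse tables, where a nominally significant result can correspond to an exact p-value of 0.11 to 0.22. The exploratory label limits the consequence but does not make such p-values valid. The Arm A response test and its stopping rule are untouched.

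**What to change.** In Section 11.0, replace the chi-square with an exact test for both arms: Fisher's exact test, with mid-P or Boschloo's test as an option named in advance, plus an exact confidence interval for the odds ratio. Add that where an arm has 2 or fewer responders, the individual marker values are listed by response and no p-value is given.

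The cost is about two sentences, with no new data or patients. The downside is that exact tests, including mid-P, are conservative at these sizes and will rarely reach significance. In stopped tables that loss is small in practice, because one or two responders cannot support a test of association anyway.

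### Arm A's only named test of marker change against response uses a yes/no cut at 25%, although the measured percentage change would support a more powerful exploratory test

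*Combined protocol and SAP*

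**What the plan says.** Section 11.0 (Statistical considerations) describes the correlative work as mainly exploratory and names one test relating a change in marker expression to clinical response, a chi-square for p70S6 kinase or 4EBP1. The coding is given as "Both response (yes/no) or decreased expression (yes/no) will be treated as binary variables". A fall counts as a decrease once it reaches 25%, whether it was measured by densitometry or by flow. No reason is given for 25%, or for one cut across two assay methods.

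The next sentence adds the mean decrease in responders and in non-responders, as description, with no test, model or interval. A similar analysis is planned for eIF4E in the ribavirin arm. No significance level, effect size or power is stated for any of this.

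The number of patients comes from the Arm A design in the same section: "A maximum of 24 evaluable patients would give 80% power to reject the null hypothesis at a significance level of .05". Accrual stops after the first stage "If there are 2 or fewer of the 9 patients have responded".

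Section 8.0 (Correlative studies) samples the markers pre-study, at day 10-11 of cycle 1, and at days 22-26 of cycles 1 and 3. It warns that cell numbers may run short at the later times and lets flow cytometry replace blotting for Akt and p70S6K when cells are scarce.

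**The concern.** To decide whether a fall reaches 25%, the laboratory must first measure the fall. The plan then tests only which side of the cut each patient lies on, so a 26% fall counts the same as a 90% fall, and a 24% fall counts as none. With at most 24 patients there is little information to spare. A real link between on-target inhibition and response is then more likely to be missed, and the result depends on a threshold whose basis is not stated. At these numbers the chi-square approximation is itself doubtful. A better test needs no further samples.

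**Working it through.** **1. The plan's own figures.** The design continues if 3 or more of the first 9 patients respond, and "The null hypothesis is rejected if 10 or more responses are observed in 24 patients". Exact binomial calculation gives:
- type I error 0.0485 at a 25% response rate;
- power 0.805 at 50%;
- probability of early stopping at 25%: 0.75⁹ + 9(0.25)(0.75⁸) + 36(0.25²)(0.75⁷) = 0.075 + 0.225 + 0.300 = 0.601.

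The stated 80%, .05 and 60% all reproduce. No power is stated for the marker test, so there is nothing of the plan's to reproduce there. Because 24 is a maximum, the chance of stopping at 9 runs from 60% (true rate 25%) to (1 + 9 + 36)/512 = 9% (true rate 50%).

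**2. Assumptions for the marker test (none is in the documents).** Two-sided 5% level; normally distributed change with equal SD; responders shifted by 1 or 1.5 SD; 20-50% of non-responders past the cut. Splits of the 24 patients: 8:16 (33% response), 10:14 (the fewest responders that reject the null) and 12:12 (50% response).

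**3. Power at 24 patients.** Simulation, 20,000 trials per setting for the chi-square (Pearson, uncorrected) and 4,000 for the exact rank-sum:

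| Responders : non-responders | Shift | Chi-square at the cut | Exact rank-sum |
|---|---|---|---|
| 8:16 | 1 SD | 40-48% | 54-57% |
| 8:16 | 1.5 SD | 66-80% | 88-89% |
| 10:14 | 1 SD | 43-48% | 61-62% |

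The smallest gap across these ranges is 54 − 48 = 6 points and the largest is 89 − 66 = 23 points. Repeat runs move individual figures by a point or two, so the loss is given as roughly 5 to 25 points. The comparison slightly flatters the chi-square: its actual size was 3.7-6.3%, against 4.4-4.9% for the rank-sum.

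A separate calculation at 12:12 and 1 SD, with half of all patients past the cut, gave Pearson 53% and Mann-Whitney 62%, a loss of 9 points. With 70% of all patients past the cut, Pearson fell to about 42%.

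**4. Expected cell counts.** For 8:16, 1 SD and 20% of non-responders past the cut, the share of responders past it is Φ(1 − 0.842) = 0.563. The expected number past the cut is 16(0.20) + 8(0.563) = 7.7, so the smallest expected cell is 8 × 7.7/24 = 2.6. Over the 8:16 and 10:14 settings the smallest expected cell is about 2.6 to 4.9, always below 5. At 12:12 it depends on the cut: 12 × 0.5 = 6 with half past it, 12 × 0.3 = 3.6 with 70% past it. If the small counts led the analyst to a Yates correction, power at 1 SD would be 19-29% in the 8:16 and 10:14 settings.

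**5. The same loss as a sample size.** At 1 SD with equal groups and 80% power, the continuous change needs 2(1.96 + 0.84)²/1² = 15.7, so 16 per group and 32 in all. Cut at the midpoint (69% against 31%), the yes/no comparison needs 26 per group and 52 in all. Both use the normal approximation.

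**6. Where the rank-sum test cannot help.** The smallest possible two-sided exact p is 2 divided by the number of ways to choose the responders:
- 2 vs 7: 2/36 = 0.056;
- 1 vs 8: 2/9 = 0.22;
- 2 vs 4, as within one Arm B dose level: 2/15 = 0.13.

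These are the splits left by an early stop at 9, or by a 3+3 cohort. At those sizes the exact test cannot reach 5% whatever the effect.

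**The case against.** The strongest reply is that nothing in the trial turns on this test. The correlative work is declared mainly exploratory, no power is claimed for it, and neither the two-stage efficacy decision nor the dose-escalation rule uses it. That stands, and it keeps the point minor. It is not a reason to prefer the weaker of two tests on the same data.

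Other parts of the defence also stand:
- A reader might infer that the continuous data are thrown away. They are not: the group means will be reported. What is missing is a test or an interval.
- A reader might infer that the cut is arbitrary or wrong. The documents show only that it is unexplained. It is fixed in advance, and Section 2.2.2 cites a decrease of at least 25% in p15 methylation from an earlier decitabine study, though for a different marker and not as the reason for this cut.
- A reader might infer that objective 1.4 depends on this test. In Section 1.0 that objective concerns baseline expression, not change.
- Normal data with a pure shift favour continuous methods. The size of the loss therefore belongs to the assumptions, not to the protocol.
- Moving to ranks does not settle how to combine densitometry with flow cytometry, or which sampling time to use. Both must be specified.

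**Conclusion.** The point holds for Arm A as a minor improvement to an exploratory analysis. At 24 evaluable patients, under the stated assumptions, the planned chi-square gives up roughly 5 to 25 points of power against an exact rank-sum test. In the 8:16 and 10:14 settings its expected counts are also too small for comfort. The direction of the loss is well supported, but its size is not known, because the documents give no effect size, SD or share of patients past the cut.

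Two stronger readings are not supported. One is that the plan loses most of its power with about 24 patients: 24 is a ceiling, marker data may be available for fewer, and even the rank-sum test reaches only 54-62% at 1 SD in the settings tabulated. The other is that the same change should be made for eIF4E in Arm B: the phase I part enters 3 to 6 patients per dose level, and Section 11.0 gives no size for the later expansion. The primary two-stage test is unaffected.

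**What to change.** In Section 11.0, for Arm A:
- State as the exploratory analysis an exact Wilcoxon rank-sum test of percentage change from pre-study, responders against non-responders, with an interval for the difference (for example Hodges-Lehmann).
- Name one sampling time. The day 10-11 sample precedes rapamycin, so days 22-26 of cycle 1 is the first that can reflect it. Against that, Section 8.0 expects cells to be scarcer by then.
- Rank densitometry and flow values separately, or stratify by method.
- Keep the 25% cut as a descriptive table.
- If accrual stops at 9 with 2 or fewer responders, report the continuous changes descriptively. Do the same for eIF4E in Arm B.

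The cost is about one extra sentence of specification and a summary slightly less simple than a yes/no table. No new patients, samples or assays are needed.

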8.0 CORRELATIVE STUDIES

Assessment of eIF4E Expression—This will be done on all patients on pre-study marrow aspirate. Light density marrow cells will be processed, and western blotting performed to determine if the AML is eIF4E positive (increased 2 to 3 Xs above normal controls). Immunohistochemistry will also be carried out with eIF4E and DAPI to document initial nuclear localization by confocal microscopy. Having this information at study entry will allow determination of ribavirin effects on eIF4E localization at subsequent sampling points and will also help us determine if some non-M4/M5 cases express this and whether this might affect rapamycin response.

Documentation of mTOR inhibition

Assays will be performed to determine the feasibility of measuring whether the biologic endpoint of mTOR inhibition has been obtained in those receiving rapmycin and whether eIF4E has been inhibited in those receiving ribavirin.

To assess eIF4E, p70S6 kinase, and 4E-BP1 phosphorylation, leukemia blasts will be isolated via Ficoll-Hypaque density gradient centrifugation, lysed with buffer containing 50 nM Tris, pH 8.0, 120 mM Na CL, 0.5% Nonidet P-40, and protease inhibitor cocktail (Roche). The protein concentration of the lysate will be determined by using the Bradford method (Bio-rad, Hercules, CA). Equal amounts of protein will be separated on a 4%-20% Tris-Glycine gel (Invitrogen) and transferred to a BioTrace PVDF membrane. Blots will be probed with primary antibody to p70S6 kinase and to 4E-BP1 (Cell Signaling, Inc). After washing and incubation with secondary antibody, immunoreactive proteins will be visualized by using the ECL Plus detection system (Amersham Biosciences). Blasts will be sampled pre-study and after day 10-11 of the first cycle and at days 22-26 of the first and 3rd cycle. It is anticipated that the number of blasts may be diminished by the latter two samplings to the point where cell numbers may become limiting in the assay, but we will attempt to determine that this endpoint has been met in the whole light density marrow population. In those cases where aspirate is a dry tap, Western analysis will be performed on peripheral blood. Antibodies for these assays will be purchased from Cell Signaling.

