If cell numbers and amounts of protein lysate allow, to assess AKT phosphorylation, leukemic blasts isolated and lysed as described above will be blotted and probed with primary antibody to Akt or phospho-AKT (Cell Signaling). After washing and incubating with secondary antibody, immunoreactive proteins were visualized by using the ECL Plus detection system (Amersham Biosciences). If cell numbers are limiting, Akt and Phospho-Akt as well as p70S6K can be detected with a flow cytometric assay. ^{23, 34}

Other Correlative Studies to Assess apoptosis, cell cycle, and Leukemia Stem Cell Phenotype

At days 0, 11, and 22-26 of the first cycle, at day 22-26 of the 3rd cycle, and at end of study, light density cells will be analyzed for cell cycle status, apoptosis, and expression of an AML progenitor/blast phenotype (CD34+, CD38-, CD123+) by FACS analysis. CFU-L assays will also be plated. Cells will also be injected into NSG mice to determine presence of an engraftable leukemia stem cell. In brief, approximately 10(6) light density marrow cells will be injected in sublethally irradiated NSG mice via tail vein in a final volume of 0.2mL of PBS with 0.5% FBS. After 6 to 8 weeks, animals will be sacrificed and bone marrow will be analyzed for the presence of human cells by evaluation of human CD45 and human CD33 by flow cytometry ^{35, 36}. Any remaining cells will be frozen for future molecular analysis of response and resistance markers.

Timing of Correlative Studies

Pre-study marrow

- a. Cells for in vitro testing (MTT or Alamar Blue assays, apoptosis, cell cycle, viability, and snap and viable freeze for future molecular analysis.)
- b. Western blots for p70S6K, 4EBP-1, Akt, and eIF4E expression (10⁷ cells) and eIF4E localization by confocal microscopy (both arms); Gli-1 expression by Western or PCR to determine if this might predict for resistance to ribavirin (Arm B only).
- c. CFU-L assay—10(6) cells
- d. NSG reconstituting assay -10(7) cells

Day 11 aspirate (cycle 1)

- a. Light density cells for apoptosis, cell cycle, and viability
- b. Western blots for p70S6K, 4EBP-1, Akt, and eIF4E and expression of downstream mediators; eIF4E localization by confocal microscopy
- c. CFU-L assay
- d. NSG reconstituting assay

Day 28 cycle 1 (same studies)

End of cycle 3 (same studies)

End of cycle 6 (same studies)

End of study marrow (recommended but optional) (same studies)

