APPENDIX 5 (ARM A) Decitabine and Rapamycin

												D	ays											
Tests	Pre	1	2	3	4	5	6	7	8	9	10	11	12	13	14	15	16	17	18	19	20- 22	22-26	28	EOS
Decitabine		X	X	X	X	X	X ¹⁰	X ¹⁰	X ¹⁰	X10	X ¹⁰													
Rapamycin							X11	X11	X11	X11	X ¹¹	X	X	X	X	X	X	X	X	X	X			
History & Physical	X	x																						
CBC w/diff & plts	X	X						X^3																
Chemistries	X	X8						X^3																
LDH	X					X		X^3																
Urate	x	x						X ⁴																
Bone marrow	X										X1												X1	X1
Flow Cytometry	X																					X		
Cytogenetic Studies	X																					X		
DIC Panel	x																							
Molecular Studies ¹⁴	X																							
Bone marrow for Correlative Studies	X ⁵ 40cc										X540cc											X540cc		
Blood for correlative studies	X ⁷ 10cc										X ⁷ 10cc											X ⁷ 10cc		
EKG/CXR	X																							
U/A, PT, PTT, Pregnancy	X																							
Chimerism	X^2																						X^2	
Rapamycin Levels		X12													X9						X ⁹			
Evaluation of Response																							X ⁶	X ⁶
Long Term Follow Up																								X ¹³

- 1. Aspirate only in cycle 1 on day 10-11 and biopsy and aspirate at days 22-26 of cycles 1 and 3 for disease assessment, and at end of study. Marrows may also be performed when clinically indicated at other times for disease assessment. Substitute peripheral blood if aspirate/marrow cannot be obtained.
- In those patients who have had an allogeneic transplant by chromosome (sex mismatched transplants) or by PCR assay. This can be done on either blood or marrow at physicians' choice.
- 3. Twice per week or as clinically indicated
- 4. As indicated clinically
- 5. 40 cc aspirate in green top (heparinized) tubes; if marrow is a dry tap, substitute 40 cc blood total
- 6. Cycles 1 and 3 only and at end of study or study discontinuation.

- 7. 10cc in green top tube.
- 8. Include cholesterol and triglycerides on day 1 of each cycle only.
- Rapamycin levels will be drawn (trough) on days 14 and 21. Patients will be asked to hold the daily dose until the level is drawn.
- 10. Decitabine is given on days 1-10 during cycle 1. In subsequent cycles, decitabine is given days 1-5.
- 11. Rapamycin starts on Day 6 starting with Cycle 2
- 12. Cycle 2 Day 1 only
- 13. Every 6 months for up to 2 years after date of last treatment
- 14. Molecular studies completed previously are acceptable if results are in the medical record.

Version date: 09Aug2017

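### The 25% marker-decrease rule does not require a patient's two samples to share assay, tissue and cell population, and two of the three permitted mismatches can track response

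*Combined protocol and SAP*

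**What the plan says.** Section 11.0 describes the analysis: "We will utilize a Chi square method to determine a correlation between clinical response and mTOR mediator inhibition". The markers tested are p70S6 kinase and 4EBP1. Response and decrease are both yes/no variables, and "decreased expression will be defined as at least a 25% decrease by densitometry or flow cytometric measurement". The mean decrease in responders and non-responders is also described, and eIF4E is handled in the same way in the ribavirin arm. No reference visit is named. The section states that "the correlative studies will be primarily exploratory".

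Section 8.0 samples blasts pre-study, around day 10-11, and at days 22-26 of cycles 1 and 3. It then allows substitutions:

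- **Assay.** "If cell numbers are limiting, Akt and Phospho-Akt as well as p70S6K can be detected with a flow cytometric assay".
- **Tissue.** "In those cases where aspirate is a dry tap, Western analysis will be performed on peripheral blood". Footnote 5 of the calendars in Appendix 5 (both arms) agrees: "if marrow is a dry tap, substitute 40 cc blood total". That footnote also applies to the pre-study sample.
- **Cell population.** "It is anticipated that the number of blasts may be diminished by the latter two samplings to the point where cell numbers may become limiting". The same sentence goes on to say that the endpoint will then be sought in whole light-density marrow.

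No section requires matched pairs, a bridging comparison between methods, or flagging of mixed pairs.

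**The concern.** A percentage decrease has a clear meaning only if both measurements are on one scale and from comparable material. Band density and fluorescence have no common unit. Marrow and blood, or isolated blasts and whole light-density marrow, can be read on the same densitometry scale and still differ for reasons unrelated to what the drug does inside a cell.

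Mismatches unrelated to response mainly add noise. Here the cell shortage that leads to flow or to whole marrow is attributed to falling blasts, and Section 7.1 defines complete and partial remission partly by marrow blast percentage. The mismatch can therefore be commoner in one of the two groups that the chi-square test compares. What is at stake is the reading of the response-by-inhibition result and of the mean decreases reported beside it.

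**Working it through.** The plan states no power, sample size or error rate for this analysis, so it has no figure to reproduce. The check compares the substitution rules and then uses assumed inputs to show what they could do.

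**1. Reach of each substitution**

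| Switch | Trigger | Tested markers reached | Tied to falling blasts in the documents? |
|---|---|---|---|
| Western to flow | limiting cell numbers | p70S6K only (Akt is covered but is not in the Section 11.0 test) | yes, through cell shortage |
| Marrow to blood | dry tap, any visit | any Western marker | no |
| Isolated blasts to whole light-density marrow | too few blasts | any Western marker | yes |

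**2. Dilution with no change per cell**

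Let blasts carry k times the normal signal and let b be the blast share of the sample. The relative signal is S(b) = 1 + (k − 1)b, and the apparent fall is 1 − S(follow-up)/S(baseline).

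Inputs: k = 2 to 3 is the Section 8.0 threshold for eIF4E positivity; using it for other markers is an assumption. Follow-up shares of 5% and 20% are the Section 7.1 limits for complete and partial remission. A baseline share of 100% assumes perfect blast isolation. The 35% baseline is the mean at enrollment in the earlier phase I study (Section 2.6).

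| k | Baseline share | Follow-up 5% | Follow-up 20% |
|---|---|---|---|
| 2 | 100% | 1 − 1.05/2.00 = 47.5% | 1 − 1.20/2.00 = 40.0% |
| 3 | 100% | 1 − 1.10/3.00 = 63.3% | 1 − 1.40/3.00 = 53.3% |
| 2 | 35% | 1 − 1.05/1.35 = 22.2% | 1 − 1.20/1.35 = 11.1% |
| 3 | 35% | 1 − 1.10/1.70 = 35.3% | 1 − 1.40/1.70 = 17.6% |

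Blast clearance alone can cross 25% or fall short of it, depending on k and on the starting share.

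**3. Misclassification by hand**

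Assume that 60% of responders and 20% of non-responders are switched, and that matched pairs show a decrease in 20% of both groups.

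- Switched pairs read as a decrease half the time: 0.6×0.5 + 0.4×0.2 = 38%, against 0.2×0.5 + 0.8×0.2 = 26%.
- Switched pairs always read as a decrease: 0.6×1 + 0.4×0.2 = 68%, against 0.2×1 + 0.8×0.2 = 36%.

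**4. False-association rate by simulation**

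Assumptions: 24 patients (the Arm A maximum), no true change, response rate 25% or 50%, log-scale noise SD 0.10 or 0.20 per measurement, uncorrected chi-square at 3.841.

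| Share switched (responders / non-responders) | Offset of the new scale | Rate |
|---|---|---|
| none | none | 0.2% to 4.5% |
| 30% / 30% | random (log SD 0.4), 26% lower or 39% lower | 2% to 5.5% |
| 60% / 10% | random (log SD 0.4) | 6% to 20% |
| 60% / 10% | 26% lower | 17% to 39% |
| 60% / 10% | 39% lower | 32% to 70% |

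Equal switching is nearly harmless to the error rate, so the inflation comes from switching that differs by response. If the new scale reads higher (log offset +0.3), responders at 60% / 10% are classed as decreased less often than non-responders (0.8% against 1.9%, or 7.3% against 14.1%, for the two noise levels). The artefact can therefore also hide inhibition.

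**The case against.** The natural reading of the rule is a decrease seen by densitometry, or one seen by flow. Nothing tells the analyst to set a fluorescence value against a band density. On that reading a patient with a Western baseline and a flow follow-up is missing, not misclassified. This is fair, but the pair is then lost for a reason linked to blast loss, and the reading does not prevent comparison of marrow with blood, or of blasts with whole marrow, within densitometry.

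Objective 1.3 names both Western blot and phospho-flow, so flow might be run at baseline in practice. The pre-study list in Section 8.0, however, assigns p70S6K to Western blot, and the flow assay appears only as a fallback.

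Section 8.0 names only a density gradient to isolate blasts and gives no purity. The two cell populations may differ less than their names suggest, which makes the 100% baseline rows an upper end.

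A reader might infer that both the assay and the tissue switch follow cytoreduction, or that every tested marker can move to flow. The documents support neither. Dry taps are not linked to cytoreduction and can occur pre-study, and the flow fallback omits 4E-BP1 and eIF4E.

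The numerical size is wholly assumed. Even 68% against 36% is about 8 of 12 against 4 of 12 if 24 patients split evenly: chi-square = 24 × (8×8 − 4×4)² / 12⁴ = 2.67, p about 0.10. This objection stands against any claim of a known magnitude.

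**Conclusion.** The concern holds as a limit on an exploratory analysis. The substitution rules allow one patient's change to be taken across assays (p70S6K only), tissues (any Western marker) or cell populations, and no rule excludes or flags such pairs. The assay and cell-population switches are tied by Section 8.0 to falling blasts, so they can track response and create or hide an association.

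Size and direction cannot be determined, because the documents give no switch rates, assay variability, between-assay offset or blast purity. The ranges above depend on assumed values and show only that the effect could be negligible or large.

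A reader might go further and infer that an observed association would be spurious, or that the efficacy conclusion is at risk. Neither follows. The bias could run either way, and the Arm A two-stage test counts clinical responses and does not use the markers.

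**What to change.** In Section 11.0, count a 25% decrease only when both samples use the same assay, tissue and cell population, and name the pre-study sample as the reference. In Section 8.0:

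- Run the p70S6K flow assay on the pre-study sample as well, so that a low-cell follow-up has a matching baseline.
- After a dry tap, compare with the scheduled pre-study blood sample where the yield is adequate. The routine draw is 10 cc but the dry-tap substitute is 40 cc, and the pre-study Western blots are listed at 10⁷ cells, so adequacy must be confirmed.
- Report unmatched pairs separately by response group, with a sensitivity analysis, because their absence may be informative.

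Matching has limits. The 35% baseline rows above apply equally to whole marrow at both visits, where a falling blast share can still mimic inhibition, so blast share should be reported beside each such pair. Paired blood may hold few blasts in recovered patients, since Section 7.1.6 requires their absence.

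The cost is one extra flow run on baseline material already collected, some SAP wording, and some pairs becoming missing. The Arm A primary test does not change.
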